## 14.3 Assessing Relationship to RSSP Drug & Study Procedures

An SI with appropriate expertise must make the determination of relationship to the investigational product for each AE. The SI should decide whether, in his or her medical judgment, there is a reasonable possibility that the event may have been caused by the investigational product or study procedures (including imaging, LP, or skin biopsy). The assessment of the relationship of an AE to the RSSP drug or study procedures is a clinical decision based on all available information at the time the event is being documented. The following definitions of the relationship between the AE (including SAEs) drug and/or the study procedure should be considered:

- Unrelated No possible relationship
  - $\circ\,$  Concomitant illness, accident, or event with no reasonable association with treatment

- The temporal relationship between study procedure and the adverse event onset/course is unreasonable or incompatible, or a causal relationship to study procedure is implausible.
- Unlikely to be Related Not reasonably related, although a causal relationship cannot be ruled out.
  - The reaction has little or no temporal sequence from administration of treatment, and/or a more likely alternative etiology exists.
  - While the temporal relationship between study procedure and the adverse event onset/course does not preclude causality, there is a clear alternate cause that is more likely to have caused the adverse event than the study procedure.
- **Possibly Related** Causal relationship is uncertain.
  - The reaction follows a temporal sequence from administration of the treatment and follows a known response pattern to treatment; the reaction could have been produced by the treatment or could have been produced by the RSSP participant's clinical state, or by other modes of therapy administered to the participant [Suspected treatment-related AE]
  - The temporal relationship between study procedure and the adverse event onset/course is reasonable or unknown, and while other potential causes may not exist, a causal relationship to the study procedure does not appear probable.
- **Probably Related** High degree of certainty for causal relationship
  - The reaction follows a temporal sequence from administration of treatment; is confirmed by discontinuation of treatment or by re-challenge; and cannot be reasonably explained by the known characteristics of the RSSP participant's clinical state (Suspected treatment-related AE)
  - The temporal relationship between study procedure and the adverse event onset/course is reasonable and other causes have been eliminated or are unlikely.
- **Definitely Related** Causal relationship is certain.
  - The reaction follows a reasonable temporal sequence from administration of treatment; that follows a known or expected response pattern to treatment; and that is confirmed by improvement on stopping or reducing the dosage of the treatment, and reappearance of the reaction on repeated exposure (Suspected treatment-related AE)
  - The temporal relationship between study procedure and the adverse event onset/course is reasonable and other causes have been eliminated.

If no valid reason exists for suggesting a relationship, then the AE should be classified as "unrelated." If there is any valid reason, even if undetermined, for suspecting a possible causeand-effect relationship between the investigational product and the occurrence of the AE, then the AE should be considered "related."

If the relationship between the AE/SAE and the investigational product is determined to be "possibly", "probably", or "definitely" related to RSSP treatment the event will be escalated to the

IMM for review and confirmation that the event should be considered related to the investigational product for the purposes of expedited regulatory reporting.

An unanticipated AE is any AE for which the specificity or severity is not consistent with the current Investigators Brochure, current Package Insert, or described in the sub protocol.

An unexpected, suspected treatment-related AE is any unexpected AE that, in the opinion of the SI or Sponsor, there is a reasonable probability that the treatment caused the event.

# 14.4 Recording Adverse Events

AEs spontaneously reported by the participant and/or in response to an open question from the site personnel or revealed by observation will be recorded during the RSSP at the investigational site. The AE term should be reported in standard medical terminology when possible. For each AE, the SI will evaluate and report the type of event, onset (date and time), resolution (date and time), intensity, causality, action taken, serious outcome (if applicable), and whether or not it caused the participant to discontinue the RSSP. Adverse Events of Special Interest will be defined within the respective drug RSSPs.

The relationship of the AE to the investigational product should be specified by the SI based on temporal relationship and his/her clinical judgment, using the definitions specified in Section 14.3.

Intensity will be assessed according to the following scale:

- Mild (awareness of sign or symptom, but easily tolerated)
- Moderate (discomfort sufficient to cause interference with normal activities)
- Severe (incapacitating, with inability to perform normal activities)

It is important to distinguish between serious and severe AEs. Severity is a measure of intensity whereas seriousness is defined by the criteria above. An AE of severe intensity may not be considered serious.

Should a pregnancy occur, it must be reported and recorded on sponsor's pregnancy form. Pregnancy in itself is not regarded as an AE unless there is a suspicion that an investigational product may have interfered with the effectiveness of a contraceptive medication.

The outcome of all pregnancies (spontaneous miscarriage, elective termination, normal birth, or congenital abnormality) must be followed up and documented even if the participant was discontinued from the RSSP and/or Master Protocol.

All reports of congenital abnormalities/birth defects are SAEs. Spontaneous miscarriages should also be reported and handled as SAEs. Elective abortions without complications should not be handled as AEs.

Medications errors and study drug use outside of what is described in the protocol, including misuse and abuse of the investigational product, must be reported and recorded as defined in each RSSP.

# **14.5 Reporting Adverse Events**

This section summarizes the procedures for eliciting reports of and for recording and reporting adverse event and serious adverse events in the Master Protocol. Additional AE/SAE reporting and stopping rules may be included in an RSSP.

#### 14.5.1 Adverse Event Reporting Requirements

Information about AEs will be collected from the signing of consent form until the end of RSSP or 30 days following the last dose of RSSP drug (whichever comes first). SIs and coordinators will be instructed to assess for adverse events at all study visits (in person and virtual), following initiation of investigational intervention, unless defined differently in each RSSP. Adverse experiences, whether observed by the SI, or elicited from or volunteered by the participant, should be recorded in the EDC.

Any AE should be followed until resolution or stabilization. AEs reported following a premature withdrawal or conclusion of participation visit should be followed for 30 days from last drug administration unless specified otherwise in the RSSP.

AEs will be reported by the site as required by the site's Institutional Review/Ethics Board.

#### 14.5.2 Serious Adverse Event Reporting Requirements

All SAEs (related and unrelated) will be recorded in a similar manner to AEs, unless further defined in the RSSP. All SAEs must be reported by the SI within one business day of the first awareness of the event. The SI must complete, sign and date the SAE pages, verify the accuracy of the information recorded on the SAE pages with the corresponding source documents, and notify the safety department.

A Medical Monitor (MM) will work closely with the site to obtain additional follow-up information, if required or available. As additional information is obtained, one or more follow-up SAE forms should be completed. SAE notifications will be provided to the sponsor MJFF and IND, Inc.

Relevant regulatory authorities must be notified by the appropriate IND holders of certain events. It is the SI's responsibility to notify the IRB or Independent Ethics Committee (IEC) of all SAEs that occur at his or her site. SIs will also be notified of all unexpected, serious, drug-related events (7/15 Day Safety Reports) that occur during the clinical trial. Each site is responsible for notifying its IRB or IEC of these additional SAEs.

## 14.6 Medical Monitor (MM)

At least one MM will be appointed for this Master Protocol. The MM will interact with all sites to ensure that sites collect as much information as possible for all reported AEs and SAEs. The MM will also serve as a liaison between the IMM and sites to collect any additional information required or requested by the IMM to complete their reviews in a timely manner. Finally, the MM will conduct protocol safety training and address any safety related questions from the CRO, study monitors, and other project team members.

# 14.7 Independent Medical Monitor (IMM)

At least one IMM will be appointed for this Master Protocol. The IMM will review all reported SAEs, AEs deemed to be severe, and AEs deemed to be treatment-related by the site in near realtime in order to evaluate them to identify the need for expedited reporting. For any such reported SAEs or AEs, the IMM will be notified to prompt a review of the event for seriousness, causality, expectedness, and additional factors which may affect reporting responsibilities. The IMM will review the SAE within 24 hours of receipt notification. If additional information is required to complete the evaluation of an SAE, the IMM may contact the MM to request more information from the site.

The unblinded statistician will provide aggregate reports of all AEs to the IMM for review on a quarterly basis (or as specified in each RSSP). These aggregate reports will summarize all AEs by severity (serious/not serious), attribution (anticipated or unanticipated), and relationship to the regimen-specific treatment. All AEs will be coded using the Medical Dictionary for Regulatory Activities (MedDRA: version 26.1). The IMM will review these quarterly reports for any trends of interest or safety signals. Should any concerns arise due to observed trends, the IMM may send a written recommendation to the unblinded statistician via email requesting that the report be forwarded to the Data and Safety Monitoring Board (DSMB) for future review, as appropriate.

## 14.8 Data and Safety Monitoring Board (DSMB)

An independent DSMB, consisting of independent experts who will review and evaluate safety data, will be assembled for the trial. A DSMB Charter will detail the processes of this group. The DSMB will receive blinded and unblinded summary reports, as specified in the DSMB Charter, consisting of the following topics:

- Performance Monitoring: A report of participant recruitment, comparison with targeted recruitment, retention, protocol adherence, and quality of data collection procedures.
- Treatment Monitoring: The DSMB will be provided data on treatment integrity and adherence.
- Safety Monitoring: The DSMB will examine data related to safety of all Master Protocol participants, including all AEs related to each RSSP study treatment. This includes a summary of the IMM's quarterly reviews since the prior DSMB meeting.

Reports will be provided for each RSSP at planned periodic meetings throughout the RSSP as specified in the DSMB Charter. The DSMB will receive separate reports per trial intervention specific RSSPs to review independently. These reports will contain data comparing the intervention to all concurrent placebo controls and the regimen-specific controls for that RSSP. The DSMB will also review data on the conduct of the Master Protocol. Meetings will be held inperson or via teleconference, depending on the preference of the DSMB Chair.

As necessary, the DSMB can review the frequencies of clinical and laboratory abnormalities. Recommendations for modification or termination of the RSSP based on safety data will be made by the DSMB to the Sponsor. The DSMB will review safety data throughout the trial and may recommend stopping enrollment into a treatment arm if safety concerns arise that lead them to determine that there is a significant difference in the rate of a particular AE that would indicate a risk that is greater than the possible benefit of the investigational product. A notable increase in

the frequency of any AE should be examined by the DSMB, although it may not lead to a recommendation.

Complete information can be found in the DSMB Charter.

# **15. STATISTICS**

### **15.1 Primary Endpoints and Analyses**

**Primary scientific question:** Does the treatment slow the rate of progression in DAT SPECT mean striatum SBR or MDS-UPDRS Part III score for those with NSD Stage 2B?

**Primary Endpoints.** To explore this question from the perspective of a biomarker and a clinical measure of symptom worsening, there are two primary endpoints: (a) DAT SPECT mean striatum SBR across time and (b) MDS-UPDRS Part III score across time. Both endpoints are measured until the final participant randomized has the opportunity to complete their 24 month follow up visit in the assigned RSSP. This results in greater than 24 months of follow up on participants randomized earlier in enrollment.

**Primary Analyses.** The Bayesian primary analysis models estimate a difference in the rate of change of each primary endpoint from baseline through last visit, comparing active treatment versus a shared concurrent and non-concurrent placebo. Analyses of treatment superiority will be performed assuming one-sided type I error of 5%. Each primary endpoint will be tested with equal priority with respect to active treatment superiority versus shared concurrent and non-concurrent placebo.

1) DAT SPECT Mean Striatum SBR. A Bayesian repeated measures model of mean striatum SBR, adjusted for baseline MDS-UPDRS part III score strata, will be used to compare the slope of active treatment versus the shared concurrent and non-concurrent placebo arm. The model allows for heterogeneity across individual baseline mean striatum SBR values and individual slopes, heterogeneity across regimens due to minor differences in the inclusion/exclusion criteria or mode of administration.

It is hypothesized that an effective treatment will decrease the progression rate and slow the decline in mean striatum SBR. A greater negative slope indicates a greater reduction in the biomarker and a greater progression rate. The following hypothesis test for a difference in slopes between active treatment and placebo groups will be conducted using the Bayesian posterior distribution.

H0: The active treatment group's average mean striatum SBR slope is equal to or less than that of the shared placebo arm.

 $\mathrm{H}_{a}\!\!:$  The active treatment group's average mean striatum SBR slope is greater than that of the shared placebo arm

If the Bayesian posterior probability of active treatment superiority  $(H_a)$  is greater than or equal to a prespecified threshold of 0.95, the null hypothesis will be rejected, and the active treatment will be deemed superior to placebo with respect to the mean striatum SBR endpoint. This decision threshold 0.95 has been calibrated to control analysis one-sided type I error at approximately 5% per regimen via simulation.

2) MDS-UPDRS Part III score. A Bayesian repeated measures model of MDS-UPDRS Part III score over time, adjusted for the baseline score strata, will be used to compare the slope of active treatment with the shared concurrent and non-concurrent placebo arm. The model allows for heterogeneity across individual baseline MDS-UPDRS Part III score values and individual slopes, heterogeneity across regimens due to minor differences in the inclusion/exclusion criteria or mode of administration.

It is hypothesized that an effective treatment will decrease the progression rate and slow the increase in symptoms as measured by MDS-UPDRS Part III score. A greater positive slope indicates faster symptom accumulation and a greater progression rate. The following hypothesis test for a difference in slopes between active treatment and placebo groups will be conducted using the Bayesian posterior distribution.

H0: The active treatment group's average MDS-UPDRS Part III slope is equal to or greater than that in the shared placebo arm.

Ha: The active treatment group's average MDS-UPDRS Part III slope is less than that of the shared placebo arm

If the Bayesian posterior probability of active treatment superiority  $(H_a)$  is greater than or equal to a prespecified threshold of 0.95, the null hypothesis will be rejected, and the active treatment will be deemed superior to placebo with respect to the MDS-UPDRS Part III score endpoint. This decision threshold of 0.95 has been calibrated to control analysis one-sided type I error at approximately 5% per regimen with simulation.

## **15.2 Randomization**

The platform trial incorporates two stages of randomization.

- 1) Equal randomization to all currently *J* actively enrolling regimens for which a participant is eligible, where regimen denotes both active treatment and placebo groups.
- 2) After confirming any additional regimen specific eligibility criteria are met, stratification by baseline MDS-UPDRS part III score (<7 vs.  $\geq$ 7), and then *J*:1 randomization within assigned regimen to either active treatment or placebo.

# **15.3 Sample Size Considerations**

Overall platform trial sample size is based on the number of regimens. The sample size for each regimen will include 125 participants on active treatment and at least 125 shared concurrent and non-concurrent control participants. To assess the required sample size, analyses were conducted using the observational cohort of participants in PPMI who meet NSD Stage 2B criteria and all eligibility criteria for the Master Protocol (based on a download of the PPMI data from 07/2024). These PPMI participants were recruited in two different cohorts: sporadic PD & prodromal. The participant's enrollment cohort significantly affects progression. Summaries of the two-year decline in the PPMI natural history data by subgroup (PD vs. prodromal) are included in Table 5 below. Assuming that 95% of the randomized participants for the P2P study are expected to come from the < 7 MDS-UPDRS Part III baseline strata, these data were used to inform assumptions for simulating virtual participant outcomes for longitudinal DAT SPECT mean striatum SBR and longitudinal MDS-UPDRS Part III.

Endpoint	PD Cohort (N = 76)	Prodromal Cohort (N = 94)
Mean Striatum SBR	-0.26 (0.17)	-0.12 (0.20)
MDS-UPDRS Part III	6.9 (8.0)	2.9 (3.9)

Table 5: Two-Year Decline in Primary Endpoints by PPMI Natural History Cohort
-------------------------------------------------------------------------------

For a specific regimen, "power" is defined as the probability of demonstrating success on at least one of the primary endpoints. The primary analysis population for each regimen includes shared concurrent and non-concurrent control participants. As a result, regimens that enter the platform trial later can be expected to see an increased power relative to that of the first regimen as a result. Assuming 95% of randomized participants within an RSSP fall into the < 7 MDS-UPDRS Part III baseline strata, Table 6 demonstrates the benefits of the stated criteria by showing the probability of success for the first regimen under various assumed true values for the change on each endpoint. The first regimen in the platform is estimated to have 74%, 84%, and 91% power to detect treatment effects when both of the endpoints achieve 30%, 35%, and 40% slowing of progression, respectively. Similarly, we have greater than 86% power to declare success if there is truly a 40% or greater reduction in slope/progression of MDS-UPDRS Part III as long as there is at least a simultaneous 30% or greater reduction in mean striatum SBR. Finally, we have around 83% or higher probability of declaring success if there is truly a 40% or greater reduction in slope/progression on the DAT SPECT imaging endpoint and at least a 30% reduction on slope/progression on the MDS-UPDRS Part III endpoint. The table also demonstrates that the overall type I error probability (probability of meeting the criteria when there is no true reduction for either endpoint) is well controlled at 10.3%. For more details about the operating characteristics for each regimen and the assumptions used to calculate power, refer to the Design Report Appendix in the P2P Statistical Analysis Plan.

UPDRS Slowing	DAT Slowing	Power
0%	0%	10.3%
0%	30%	49%
0%	40%	67%
0%	50%	82%
30%	0%	56%
30%	30%	74%
30%	40%	83%
30%	50%	91%
40%	0%	77%
40%	30%	86%

Table 6: Overall RSSP Power (Win on Either Endpoint)

40%	40%	91%
40%	50%	94%
50%	0%	92%
50%	30%	95%
50%	40%	97%
50%	50%	98%

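### The primary models name no term for PPMI enrolment cohort, which the protocol says affects progression; the main exposure is in later regimens that pool non-concurrent controls

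*Protocol*

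**What the plan says.** Section 15.3 describes the natural-history data behind the sample size: "These PPMI participants were recruited in two different cohorts: sporadic PD & prodromal". It adds that "The participant's enrollment cohort significantly affects progression". Table 5 gives the two-year change by cohort (PD N = 76, prodromal N = 94):

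- Part III: 6.9 (8.0) versus 2.9 (3.9)
- Mean striatum SBR: -0.26 (0.17) versus -0.12 (0.20)

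Section 15.1 names one covariate for each primary model. The SBR model is "adjusted for baseline MDS-UPDRS part III score strata, will be used to compare the slope of active treatment" with pooled placebo. The other is "A Bayesian repeated measures model of MDS-UPDRS Part III score over time, adjusted for the baseline score strata". Both also allow for individual baseline values, individual slopes and heterogeneity across regimens, the last attributed to small differences in eligibility criteria or route of administration.

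The same Part III split (<7 versus ≥7) is the only stratification factor (Sections 8.2.1 and 15.2). Section 15.3 assumes that "95% of the randomized participants for the P2P study are expected to come from the < 7 MDS-UPDRS Part III baseline strata".

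On controls, "The sample size for each regimen will include 125 participants on active treatment and at least 125 shared concurrent and non-concurrent control participants". Section 15.5 draws them from every control arm of every regimen, provided the person met the initial eligibility for the regimen being analysed. Neither Section 15.1, Section 15.2 nor the Synopsis names enrolment cohort or an enrolment-period term as a covariate or stratum. No expected PD/prodromal mix is given.

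**The concern.** The protocol identifies a baseline factor that drives the slope being tested, then names a different factor for adjustment without linking the two. Section 7 excludes neither cohort.

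Within concurrently randomised arms this affects only precision. Non-concurrent controls are different, because randomisation does not balance them against the active arm. If they contain more fast-progressing PD-cohort participants, the pooled placebo slope is steeper for reasons unrelated to treatment, and an inactive drug looks better than placebo. The platform is perpetual and the control pool has no stated time limit, so this bears on every regimen after the first.

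**Working it through.** **Inputs.** Means, bracketed figures and cohort sizes from Table 5; 125 per arm and the power figures from Section 15.3; one-sided 5% per endpoint from Section 15.1. Assumptions: bracketed figures are SDs; two-year change stands in for the slope model; endpoints are independent; no dropout; PD share p is ranged because it is not stated.

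**1. Size of the cohort effect.**
- Part III: difference 4.0, SE √(8.0²/76 + 3.9²/94) = 1.00, z = 4.0; ratio 6.9/2.9 = 2.4.
- SBR: difference 0.14, SE √(0.17²/76 + 0.20²/94) = 0.028, z = 4.9; ratio 0.26/0.12 = 2.2.

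Table 5 supports the protocol's statement.

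**2. Reproducing the stated power.** For PD share p, the mean change is p·m₁ + (1−p)·m₀. Its variance is p·s₁² + (1−p)·s₀² (within cohort) plus p(1−p)d² (between cohorts). At p = 5%:
- Part III: mean 3.10; variance 17.65 + 0.76 = 18.41 (SD 4.29).
- SBR: mean 0.127; SD 0.201.

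Power at 30% slowing is Φ(0.3·mean/√(2·variance/125) − 1.645):
- Part III: Φ(0.930/0.543 − 1.645) = 52.7%.
- SBR: Φ(0.0381/0.0254 − 1.645) = 44.2%.
- Either endpoint: 1 − 0.473 × 0.558 = 73.6% (stated 74%).

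At 35% and 40% slowing the results are 83.4% and 90.6% (stated 84% and 91%). Fourteen of the 16 rows of Table 6 fall within 2 points, and the largest gap is 2.7. A 7.5% share also fits 14 rows. At the 45% PD share of the planning data (76/170) only 6 rows fit; for example, 30% slowing on DAT alone gives 71.5% against 49% stated. The null row gives 1 − 0.95² = 9.75% against 10.3% stated, which was obtained by simulation.

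**3. Precision lost by omitting cohort.** Replace total variance by within-cohort variance; 30% slowing on both endpoints:

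| PD share | Variance explained, Part III / SBR | Power without cohort | Power with cohort |
|---|---|---|---|
| 5% | 4% / 2% | 73.6% | 74.8% |
| 20% | 9% / 8% | 77.3% | 80.1% |
| 45% | 10% / 12% | 86.1% | 89.2% |

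**4. Error if the mix differs in non-concurrent controls.** Take 125 active and 125 concurrent controls at 5% PD, plus 125 non-concurrent controls with a PD share higher by δ, and no model term absorbing the shift. Half the pooled controls are shifted, so bias = (δ/2)·d, and error = Φ(bias/SE − 1.645). At δ = 10 points:
- Part III: bias 0.05 × 4.0 = 0.20, SE 0.483, error Φ(0.414 − 1.645) = 10.9%.
- SBR: bias 0.05 × 0.14 = 0.007, SE 0.022, error Φ(0.318 − 1.645) = 9.2%.

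| δ | Part III bias (share of a 30% effect) | Part III error | SBR error |
|---|---|---|---|
| +5 points | 0.10 (11%) | 7.6% | 6.9% |
| +10 points | 0.20 (22%) | 10.9% | 9.2% |
| +20 points | 0.40 (43%) | 20.1% | 15.6% |
| −5 points | −0.10 | 3.1% | 3.6% |

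With 250 non-concurrent controls and δ = 10 points, the errors are 14.5% and 11.6%. With concurrent controls only, the bias is zero.

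**5. Could the Part III stratum stand in for cohort?** If every ≥7 participant (5%) belonged to the PD cohort, the stratum would carry at most 0.05(1−p)/(0.95p) of the cohort variance: 100% at p = 5%, 47% at 10%, 21% at 20% and 6.5% at 45%.

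**The case against.** **Model terms.** The models contain more than the stratum. Individual slopes put between-person variation into the variance, but they do not correct a difference in group means. Regimen heterogeneity might absorb a mix change that follows regimen, which is why step 4 is conditional. Its stated purpose is eligibility and administration differences, and a drift within one long-running regimen would escape it.

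**Proxy.** If about 5% of participants are from the PD cohort and these are largely the ≥7 group, the stratum already does most of the work. A reader might infer from the 95:5 split that the stratum explains almost nothing. Step 5 shows that this does not follow. The protocol neither claims nor excludes the proxy role.

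**The 45% mix.** A reader might take the planning data's 45% PD share and conclude that omitting cohort costs the equivalent of 11–14% of the sample. The documents do not support this: the Synopsis describes the target group as formerly prodromal, and Table 6 fits a share of about 5–7.5%.

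**Chance imbalance.** A reader might also treat a chance cohort imbalance between randomised arms as bias. It is random error already inside the 5%. At 5% PD its SE is √(2 × 0.05 × 0.95/125) = 2.8 points, so a 10-point imbalance is unlikely.

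**Left to the SAP.** Section 15.3 refers operating characteristics and power assumptions to an SAP appendix that is not at hand, and the full model may be there. That part stands. The protocol does, however, name its adjustment factor, and it should be the right one or be justified as a proxy.

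**Conclusion.** The point holds as a missing adjustment whose main consequence is conditional. For the first regimen, and for any comparison with concurrent controls, there is no bias; the cost is about 1 point of power at 5% PD and about 3 points at 20–45%. For a later regimen with equal numbers of concurrent and non-concurrent controls, a 10-point excess of PD-cohort participants among the non-concurrent ones would raise the one-sided error per endpoint from 5% to about 9–11%, unless the regimen term absorbs it.

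A reader might infer that such drift is expected, since Section 5.1 describes PPMI expanding its prodromal cohort from about 1400 towards 2000. That does not establish a changing mix within P2P, and the protocol reports none. It is a risk to guard against, not a demonstrated inflation. The sizes rest on the assumptions listed with the calculation, chiefly the unstated PD share.

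**What to change.** In Section 15.1, add PPMI enrolment cohort (sporadic PD versus prodromal) and a cohort-by-time slope term to both Bayesian models. Keep the Part III strata as the randomisation factor and covariate. Re-run the simulation that calibrates the 0.95 threshold under the revised models, and include a scenario in which the PD/prodromal mix differs between non-concurrent controls and the active arm. State the assumed mix in Section 15.3.

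No new data collection should be needed, since every participant comes from PPMI. The costs are the recalibration and an imprecise cohort slope if few PD-cohort participants enrol: at 5% that is about 6 of 125 per arm, possibly overlapping with the ≥7 stratum. Cohort adjustment addresses this one source of drift; it does not deal with other calendar-time changes among non-concurrent controls.
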